#### **8.4 Assessment of causality**

The following categories and definitions for assessing the causal relationship of an event to the investigational product(s) are provided as a guide to be used for every event reported in Eli Lilly & Co. clinical trials:

- Definite/Certain: there is a reasonable causal relationship between the investigational product(s) and the AE; the event responds to withdrawal of the

investigational product(s) (de-challenge) and recurs with re-challenge when clinically feasible.

- Probable: there is a reasonable causal relationship between the investigational product(s) and the AE; the event responds to de-challenge; re-challenge is not required.
- Possible: there is reasonable causal relationship between the investigational product(s) and the AE; de-challenge information is lacking or unclear.
- Not Likely: There is a temporal relationship to study drug administration, but there is not a reasonable causal relationship between the study drug and the AE.
- Unrelated: there is not a temporal relationship to the investigational product(s) administration (too early, late, or the investigational product was not taken) or there is a reasonable causal relationship between another drug, concurrent disease, or circumstance and the AE.

## **8.5 *Collection of safety information***

Pre-existing toxicities will be collected and noted on patient's medical record.

Additionally, collection of AE information will be performed from the time the patient receives the initial infusion of the study drug(s), and must continue throughout the study until 30 days after the last dose, unless specified otherwise in the protocol. This includes pre-existing conditions or symptoms that worsened during the study, or whose relationship to the investigational product changed, but does not include pre-planned hospitalizations or procedures for pre-existing conditions. In addition, the investigator should notify Eli Lilly & Co. of any SAE or outcome that may occur after this time period that he/she believes to be related to IMC-A12 and/or cetuximab. An AE report must contain the following four basic elements: (1) an identifiable patient; (2) a suspect medicinal product; (3) an identifiable reporting source; and (4) an identifiable event or outcome. All identified AEs must be recorded and described in patient's medical record. If known, the diagnosis of the underlying illness or disorder should be recorded in

addition to the presenting symptoms. The following information should be captured for all AEs: the date of the onset and resolution; the severity of the event as determined by PI or study collaborator (see definitions in NCI-CTCAE, Version 3.0); the investigator's opinion of the relationship of the event to the investigational drug/s (certainly/definitely, probably, possibly, unlikely, or not related); the treatment required for the AE; information regarding resolution/outcome; and if the AE is serious, a clear identification of the seriousness outcome.

## ***8.6 Reporting Product Complaints***

ImClone collects product complaints on study drugs used in clinical trials in order to ensure the safety of study participants, monitor quality, and to facilitate process and product improvements.

Complaints related to unblinded comparator drugs or concomitant drugs are reported directly to the manufacturers of those drugs in accordance with the package insert.

The investigator or his/her designee is responsible for handling the following aspects of the product complaint process in accordance with the instructions provided for this study:

- Recording a complete description of the product complaint reported and any associated AEs using the study-specific product complaint form provided by ImClone for this purpose
- E-mailing the completed product complaint form within 24 hours to ImClone or its designee as listed on the product complaint form

If the investigator is asked to return the product for investigation, he/she will return a copy of the product complaint form with the product.

## ***8.7 Expectedness***

The IMC-A12 Investigator's Brochure will be updated periodically to include new and relevant safety information. Until such time that an AE becomes identified in the Investigator's Brochure, it should be considered unexpected, regardless of whether the AE has been reported in a previous IND Safety Report.

## **8.8 Clinical significance**

### **8.8.1 Pregnancy**

Women of childbearing potential (WOCBP) and fertile men with partners of childbearing potential must be using an adequate method of contraception to avoid pregnancy throughout the study and for up to 4 weeks after the study in such a manner that the risk of pregnancy is minimized.

WOCBP include any female who has experienced menarche and who has not undergone successful surgical sterilization (hysterectomy, bilateral tubal ligation, or bilateral oophorectomy) or is not postmenopausal (defined as amenorrhea  $\geq 12$  consecutive months or women on hormone replacement therapy with documented serum follicle stimulating hormone level  $\geq 35$  mIU/mL). Even women who are using oral, implanted, or injectable contraceptive hormones or mechanical products, such as an intrauterine device or barrier methods (e.g., diaphragm, condoms, spermicides), to prevent pregnancy, are practicing abstinence, or whose partner is sterile (e.g., vasectomy), should be considered to be of childbearing potential.

WOCBP must have a negative serum or urine pregnancy test at baseline. Sexually active WOCBP must use an effective method of birth control during the course of the study, in a manner such that the risk of failure is minimized.

Prior to study enrollment, WOCBP must be advised of the importance of avoiding pregnancy during trial participation and the potential risk factors for an unintentional pregnancy. This discussion will be documented on the informed consent form required for study participation.

In addition, all WOCBP or fertile men with partners of childbearing potential should be instructed to contact the investigator immediately if they suspect they or their partner

might be pregnant (eg, missed or late menstrual period) at any time during study participation.

If following initiation of study treatment, it is subsequently discovered that a trial patient is pregnant or may have been pregnant at the time of exposure to IMC-A12 and/or cetuximab, including during at least 6 half-lives after product administration, IMC-A12 and cetuximab will be permanently discontinued in an appropriate manner.

Protocol-required procedures for study discontinuation and follow-up must be performed on the patient unless contraindicated by pregnancy (e.g., x-ray studies). Other appropriate pregnancy follow-up procedures should be considered if indicated. In addition, the investigator must report to Eli Lilly & Co. follow-up information regarding the course of the pregnancy, including perinatal and neonatal outcome. Infants should be followed for a minimum of 8 weeks.

## **8.9 Clinical laboratory adverse event**

All laboratory test values captured as part of the study should be recorded on the appropriate source documents.

Abnormal laboratory tests will be considered clinically significant and will be documented in the adverse event record only if any of the following are true:

- Results in patient withdrawal from study participation
- Requires treatment and/or medical intervention (such as a treatment hold or dose reduction)
- Has clinical manifestations which are considered by the investigator as medically important

It is expected that wherever possible, the **clinical, rather than the laboratory term**, will be used by the reporting investigator (e.g., “anemia” is preferable to “a low hemoglobin value”), unless otherwise specified in this protocol.

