### **9.2.2 Hyperglycemia (Diabetes)**

For the assessment of hyperglycemia (diabetes), both the NCI-CTCAE Version 3.0 Endocrine (pancreatic endocrine: glucose intolerance / diabetes) and Metabolic / Laboratory (glucose, serum-high / hyperglycemia) terms should be used. If hyperglycemia/diabetes occurs during treatment with IMC-A12, treatment is dependent upon symptom severity. For grade 1 or 2 hyperglycemia (fasting glucose < 250 mg/dL),

IMC-A12 treatment should continue; oral agents or insulin may be used as clinically indicated.

For grade 3 hyperglycemia (fasting glucose 250-500 mg/dL), IMC-A12 treatment may continue if the patient is asymptomatic and glucose < 300mg/dL; insulin may be initiated. IMC-A12 and cetuximab should be discontinued for grade 3 hyperglycemia if there are symptoms interfering with ADL or if glucose is  $\geq$  300mg/dL

For grade 4 hyperglycemia (fasting glucose >500 mg/dL), IMC-A12 and cetuximab therapy should be discontinued.

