### **12.2.4 Safety**

The toxicity associated with each treatment arm will be observed and characterized; toxicity will be reported by type, frequency, and severity, as determined in section 8.

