### **12.6.2 *Interim safety analysis***

The combination of cetuximab and IMC-A12 has not been extensively assessed in human subjects. Because of the different anticancer mechanisms and non-overlapping clinical toxicities of these agents, it is not anticipated that the toxicity of this combination therapy will significantly exceed that observed with IMC-A12 or cetuximab monotherapy or present an undue risk to patients. Additionally, the combination of cetuximab and IMC-A12 was not associated with enhanced toxicity in preclinical in vivo studies.

Nonetheless, the potential for unforeseen or additional toxicity exists with any novel combination. Hence, as added precautions, in the event that new safety signals are detected, or the incidence of serious adverse events exceeds that expected of the component drugs within the combination therapy, consideration will be given to protocol modification, termination, or additional safety review at specified time-points before accrual is completed.

A Bayesian toxicity monitoring rule will be applied in each arm separately to ensure patient safety. However, all toxicities across all arms will be examined together as well for identifying the patterns of toxicity to provide further protection of patient safety. It is defined that an acceptable target toxicity level is no more than 30% of the patients experiencing dose limiting toxicity (DLT, defined as grade 3–4 toxicities, except for hypersensitivity reactions and grade 3 skin toxicity and fatigue). If at any given time, the probability that the DLT rate exceeds the 30% target is high (probability  $> 0.8$ ), consideration will be given to modifying the protocol accordingly. Assuming that the probability of DLT has a vague prior of beta (0.3, 0.7), the posterior distribution of the DLT rate is also a beta. The “stopping boundaries” (i.e., holding for new patients randomization) are 3/6, 4/8, 5/11, 6/14, 7/17, and 8/20 where “a”/“b” indicates “a” patients experiencing a DLT among the first “b” patients. In other words, in each given arm we will hold randomization for new patients if the number of DLTs given the number of patients treated is **greater than or equal to** the boundaries indicated above.

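### Section 8.9 admits laboratory abnormalities to the adverse event record by consequence, while DLTs are defined by grade, so some untreated grade 3-4 values can be missing from the toxicity tables and possibly from the DLT count

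*Combined protocol and SAP*

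**What the plan says.** - **Recording (section 8.9).** An abnormal laboratory test "will be documented in the adverse event record only if any of the following are true". The three conditions are withdrawal from the study, a need for treatment or intervention, and clinical manifestations that the investigator finds medically important. The second condition reads "Requires treatment and/or medical intervention (such as a treatment hold or dose reduction"; a held dose is therefore enough. Raw values are kept regardless: "All laboratory test values captured as part of the study should be recorded on the appropriate source documents".
- **Glucose (section 9.2.2).** Fasting glucose of 250-500 mg/dL is grade 3. In that range "IMC-A12 treatment may continue if the patient is asymptomatic" and glucose is below 300 mg/dL, with insulin optional. At 300 mg/dL or above, or with symptoms that limit daily activities, both drugs are stopped.
- **Other toxicity (section 10.1).** For grade 3 toxicity that the investigator does not consider clinically significant, the dose is withheld.
- **Tables (section 12.2.4).** "toxicity will be reported by type, frequency, and severity, as determined in section 8".
- **Monitoring (section 12.6.2).** The rule is applied per arm, and "an acceptable target toxicity level is no more than 30% of the patients experiencing dose limiting toxicity". A DLT is "defined as grade 3–4 toxicities, except for hypersensitivity reactions and grade 3 skin toxicity and fatigue". Randomization is held when "the probability that the DLT rate exceeds the 30% target is high", meaning above 0.8.

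**The concern.** Section 8.9 filters laboratory findings by what followed from them. Section 12.6.2 classifies toxicity by grade and exempts no laboratory value. The same glucose result can thus be a DLT under one section and absent from the adverse event record under the other.

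For an asymptomatic patient between 250 and 300 mg/dL, the deciding factor is whether a physician chose to treat. The trial is open-label (section 4.1), so that choice is made with the arm known. Section 6.10.2 describes hyperglycemia as the most common and clinically relevant toxicity of IGF-1R inhibitors seen so far. At stake are the completeness of the grade 3-4 laboratory rates by arm and the reproducibility of the DLT count behind the hold rule: two teams with the same patients could count different numbers.

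**Working it through.** **1. Which grade 3-4 values escape section 8.9?**

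| Finding | What the plan has happen | Meets an 8.9 condition? |
|---|---|---|
| Fasting glucose 250 to <300 mg/dL, no symptoms, no insulin or oral agent | Treatment may continue (9.2.2) | No |
| Same value, insulin or oral agent given | Treated | Yes |
| Glucose ≥300 mg/dL, or limiting symptoms, dose still due | Drugs stopped (9.2.2) | Yes |
| Grade 3 magnesium, dose still due, judged not clinically significant | Dose withheld (10.1) | Yes, a hold |
| Grade 3-4 value first found at the pre-surgery draw, untreated, no important manifestations | Normally no dose left to hold | No |

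The last row follows from the schedule. Doses fall around days -9 and -2 (section 4.1). The final protocol laboratory tests are on the day of surgery or up to 2 days before (section 7.3). The events table in section 7.5 marks no adverse event assessment at that visit and no chemistry at follow-up.

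**2. Reproducing the plan's boundaries.** Inputs from section 12.6.2 are the prior beta(0.3, 0.7), target 0.30 and trigger 0.8. With *a* DLTs among *b* patients the posterior is beta(0.3 + *a*, 0.7 + *b* − *a*), and the quantity needed is P(rate > 0.30). For 3/6 this is beta(3.3, 3.7); for 2/6 it is beta(2.3, 4.7).

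| Boundary | P(rate > 0.30) | With one DLT fewer |
|---|---|---|
| 3/6 | 0.8169 | 0.5255 |
| 4/8 | 0.8593 | 0.6383 |
| 5/11 | 0.8390 | 0.6432 |
| 6/14 | 0.8262 | 0.6491 |
| 7/17 | 0.8178 | 0.6554 |
| 8/20 | 0.8122 | 0.6617 |

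All six stated boundaries reproduce. With one event fewer, every one falls below 0.8.

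**3. Effect on the chance of a hold, if DLTs are counted from the adverse event record.** The share unrecorded is not in the documents, so it is varied as an assumption. Recorded rate = true rate − unrecorded points. The chance of reaching a boundary within 20 patients comes from an exact binomial recursion at the six stated looks.

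| True DLT rate | None unrecorded | 5 points | 10 points | 15 points |
|---|---|---|---|---|
| 45% | 84.5% | 72.8% | 57.8% | 41.4% |
| 40% | 72.8% | 57.8% | 41.4% | 26.1% |

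**The case against.** Much of the opposing case stands.

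- **Magnesium.** A reader might infer that any grade 3 magnesium value not repleted is lost, and might apply the 10-15% severe hypomagnesemia in section 9.1.5 to 20 patients to get 2 to 3 per arm. The documents do not support this. While a dose is due, section 10.1 withholds it and section 8.9 records a hold, so the value is normally captured. What remains is values found after the last dose, or cases where the investigator uses the discretion in section 10.1 not to hold. The 10-15% comes from other trials with onset of days to months, whereas this trial gives two or at most three doses, and Arm B receives no cetuximab.
- **Glucose.** The window is narrow. Section 1.3.2.1 describes phase I rises of around 350 mg/dL that responded to oral agents; treated cases like these would be recorded. Section 10.1 names hyperglycemia as an exception only in its discontinuation sentence. If its withholding sentence were read to cover glucose, a hold would be recorded, but that reading conflicts with section 9.2.2, and the passages must be reconciled.
- **The DLT count.** Loss from it is an inference. Section 12.6.2 names no data source, section 8.3.1 allows a laboratory finding to be an adverse event, and section 9.2.2 calls for the CTCAE laboratory term. These pull against section 8.9 without overriding its restriction.
- **The glucose objective.** Section 12.5 plans repeated measures analysis of serum glucose, which does not depend on the adverse event record.
- **The boundary example.** Any missed event would remove a hold at a boundary. The example shows sensitivity to a single event and says nothing about how often section 8.9 causes one.

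None of this closes the two gaps in the toxicity tables.

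**Conclusion.** The point holds in limited form and is worth correcting. Followed as written, sections 8.9 and 12.2.4 allow two groups of events to be left out of the toxicity tables: asymptomatic, untreated fasting glucose of 250 to below 300 mg/dL, and untreated grade 3-4 values without important manifestations first found at the pre-surgery draw. Whether they also leave the DLT count depends on a data source that section 12.6.2 does not state.

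The number of events affected cannot be derived from the documents. What can be shown is that one uncounted DLT at any boundary removes the hold, and that at an assumed true rate of 45% the chance of a hold falls from 84.5% to between 72.8% and 41.4% if 5 to 15 percentage points go unrecorded. That range illustrates an assumption and does not estimate the loss. A reader might go further and conclude that recorded rates are certainly biased down or differ between arms. The documents establish only that recording can depend on a treatment choice made with the arm known.

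**What to change.** 1. In section 12.2.4, derive CTCAE v3.0 grades from all protocol chemistry and hematology values, and tabulate the worst post-baseline grade per patient by arm, whether or not the abnormality was treated.
2. In section 12.6.2, state that the DLT count uses these derived grades, or name the laboratory values that do not count.
3. Reconcile sections 8.9, 9.2.2, 10.1 and 12.6.2 accordingly. Section 8.9 can remain as the rule for which laboratory findings are written up as adverse events.

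The cost is some programming. The values are already required on source documents, and CTCAE v3.0 is already the grading reference (section 8.10). No dose, visit or boundary changes. The downside is somewhat more counted grade 3 events, and so possibly earlier holds if derived grades are used for DLTs.

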## **8.10 Handling of serious adverse events**

In addition to the information provided above, adverse events classified as “serious” must be recorded on the MDACC Internal Adverse Event Reporting Form and reported to the Sponsor (Safety Project Manager ORE&RM) and to Eli Lilly & Co. to comply with regulatory requirements. These SAEs will include deaths, regardless of their causal relationship to investigational product. All SAEs must be reported using the MDACC Internal Adverse Event Reporting Form. To the extent possible, the descriptive terminology and other SAE attributes entered on the MDACC Internal Adverse Event Reporting Form should approximate similar information in the patient’s medical record. Study site personnel must alert Lilly or its designee of any **serious** adverse event (SAE) within 24 hours of investigator awareness of the event via a Sponsor-approved method. Alerts issued via telephone are to be immediately followed with official notification on study-specific MDACC Internal Adverse Event Reporting Form. The completed MDACC Internal Adverse Event Reporting Form must be faxed to Lilly’s Global Product Safety Fax Number for all SAEs for Cetuximab and IMC-A12 at [contact] or [contact] within 24 hours of the study site personnel’s initial notification/awareness of the event. Duly authorized study site personnel may sign completed forms; however, it is recommended that the investigator sign each final SAE report.

Collection of complete information concerning SAEs is extremely important. Thus, follow-up information that becomes available as the SAE evolves, as well as supporting documentation (e.g., hospital discharge summaries, additional lab and test results, autopsy reports, etc), should be collected subsequently, if not available at the time of the initial report, and immediately sent to Eli Lilly & Co. using the same procedure as the initial SAE report.

For ease of analysis, worldwide standardization, and regulatory reporting, Eli Lilly & Co. will code each reported adverse event or symptom to its corresponding preferred term and body system/organ class in the Medical Dictionary for Regulatory Activities version

adopted for the study. The NCI-CTCAE, Version 3.0, will serve as the reference document for determining/grading the severity or toxicity grade of all adverse events and other symptoms, with the exception of grade 4 infusion reaction (see Section 9.1.1 and 9.2.1). For AEs whose toxicity grading is not contained within the NCI-CTCAE Version 3.0 toxicity criteria, the principal investigator will be responsible for assessing severity based on the intensity of the event as it presented. Severity will be graded as mild (grade 1), moderate (grade 2), severe (grade 3), or very severe (life threatening – grade 4). Eli Lilly & Co. recommends that investigators and study site personnel enter the adverse event term on the patient's medical record and MDACC Internal Adverse Event Reporting Form as accurately as possible, regardless of the NCI-CTCAE Version 3.0 terminology for the event. The NCI-CTCAE Version 3.0 should only be used to assign the intensity/severity of the event as described above.

## **9 Treatment emergent adverse events**

Patients will be closely monitored for treatment-related adverse events, especially infusion reactions. Adverse event monitoring will occur on a continuous basis for the duration that patients are on study therapy. In addition to the planned evaluations during follow-up visits, patients will be instructed to call their physician to report any adverse events between visits.

### **9.1 *Cetuximab***

The two significant adverse events occurring most commonly in cetuximab-treated patients are infusion reactions and acneiform rash. Other adverse events associated with cetuximab include asthenia, nausea, vomiting, diarrhea, hypomagnesemia, and fever.

#### **9.1.1 *Cetuximab infusion reactions***

Infusion reactions may occur during a cetuximab infusion or may be delayed until any time after the infusion. Infusion reactions will be defined according to the NCI-CTCAE, Version 3.0, definition of allergic reaction/hypersensitivity, as follows:

- NCI-CTCAE Grade 1: transient flushing or rash, drug fever  $<38^{\circ}\text{C}$ 
  - ✓ Treatment: decrease the cetuximab infusion rate by 50% and monitor closely for any worsening.
- NCI-CTCAE Grade 2: rash, flushing, urticaria, dyspnea, drug fever  $\geq 38^{\circ}\text{C}$ 
  - ✓ Treatment: stop the cetuximab infusion, administer appropriate therapy, and then restart the cetuximab infusion with a decrease in the infusion rate of 50% and monitor closely for any worsening.
- NCI-CTCAE Grade 1 or 2 Infusion Reaction manifesting only as a delayed drug fever (starting after the end of cetuximab infusion)
  - ✓ Treatment: maintain the cetuximab dose and infusion rate and consider administering acetaminophen or cyclooxygenase-2 inhibitors (at the dose and schedule of the investigator's discretion) prior to the subsequent cetuximab infusion, if not otherwise contraindicated in the patient.
- NCI-CTCAE Grade 3 or 4 Infusion Reaction
  - ✓ A grade 3 reaction consists of: symptomatic bronchospasm with or without urticaria, requiring parenteral medication(s); allergy-related edema/angioedema; hypotension.
  - ✓ A grade 4 reaction (anaphylaxis) is a life-threatening event characterized by rapid onset (often within minutes) of airway obstruction (bronchospasm, stridor, hoarseness), urticaria, and/or hypotension.

Treatment of a Grade 3 or 4 Infusion Reaction:

- Stop the cetuximab infusion immediately and disconnect infusion tubing from the patient.
- Administer epinephrine, bronchodilators, antihistamines, glucocorticoids, intravenous fluids, vasopressor agents, oxygen, etc, as medically indicated.

Following a grade 3 or 4 infusion reaction, the patient is to receive no further cetuximab or IMC-A12 treatment. In the event of a grade 1 or 2 infusion reaction, the cetuximab infusion rate should be permanently reduced by 50%.

If there is any question as to whether an observed reaction is an infusion reaction of grades 1 to 4, the Eli Lilly & Co. Medical Monitor should be contacted immediately to discuss and grade the reaction.

